## 14 STATISTICAL ANALYSIS

### 14.1.1 Sample Size Considerations

This is a pilot safety study; therefore, sample size is not determined by power analysis. Up to 45 subjects will be recruited to the study.

### 14.1.2 Primary Analysis Set

The primary objective of the study is to establish the safety of the Check-Cap C-Scan system. The primary analysis set for establishing the safety of the Check-Cap C-Scan system will include all subjects who underwent C-Scan procedure per protocol.

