### 10.3 Primary Safety Outcome Measure

The safety of the Check-Cap System will be evaluated by the incidence of device or procedure related Serious Adverse Events (SAE), as adjudicated by the Independent Physician Adjudicator.

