## 12.4 Withdrawal Criteria

Subjects may withdraw from the study at their own request at any time.

The investigator may withdraw a subject from the study at any time for the following reasons:

- a. Severe side effects clearly related to the study device or procedure
- b. Less than adequate compliance with the study routine
- c. Presence or appearance of exclusion criteria
- d. Refusal to undergo 'post' colonoscopy
- e. A significant protocol violation
- f. At the specific reasonable request of the sponsor

The sponsor must be informed in each withdrawal case within 24 hours. The reason for withdrawal has to be recorded in the subject's file.

CONFIDENTIAL

The information contained in this document is confidential and the sole property of "Check-Cap"  
Any reproduction in part or whole without the written permission of "Check-Cap" is prohibited

	Document Title	Clinical Investigational Plan For Study CL-SY-02-0096		
	Document No.	DOC001593		Revision 03

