### 14.1.3 Operational Analysis Set

Technical or operational failures that will be discarded from the trial statistical analysis will include all cases where the system did not function as expected:

- Capsule operational failure.
- Track operational failure.
- Subject's noncompliance with procedure requirements

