  - If communication is still interrupted or missing, contact the technical support to consult about potential malfunctions and interventions.
  - If the problem is not resolved and the communication is missing - have the patient come to the clinic
  - There is no reason to assume there is a safety malfunction, but since the procedure is not yielding any additional valuable clinical data, it is recommended to take steps to expel the capsule out.
  - The clinic team (technician and/or physician) should perform, in case the capsule has not been excreted and collected already, abdominal X-Ray to assure the capsule location within the GI tract.
  - Intervention, based on the physician's decision and imaging of the capsule's location, may include: use of laxatives, fibers, removal by colonoscopy, or by surgery.
- **Technical Malfunction – C-Scan® Track Sent a Fault Indication**
  - Verify that the auditory indication was from the C-Scan® Track and not a background noise. A C-Scan® Track safety fault indication is identified by a series of repeated beeps.
  - Ask the subject if a single indication was received, or was it repeated at regular intervals.
  - Ask if the subject feels any discomfort.
  - If it is a Safety malfunction (risk of higher than usual body radiation exposure), have the subject come to the clinic ASAP and no later than 48 hours post call.
  - If the capsule has not already been excreted and collected, the clinic team (technician and/or physician) should perform abdominal X-Ray to assure the capsule location within the GI tract.
  - In the case of Safety Malfunction, intervention is required to remove the capsule without delay (recommended within 24 hours). Intervention, based on the physician's decision and imaging of the capsule's location, may include: use of laxatives, fiber supplements, removal by colonoscopy, or by surgery.

	Document Title	Clinical Investigational Plan For Study CL-SY-02-0096		
	Document No.	DOC001593	Revision	03

- Efforts should be made to minimize the subject's exposure by removing the capsule out of the body.

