#### 16.1.2 Serious Adverse Event

An SAE is any adverse event that:

- Led to death
- Led to a serious deterioration in the health of the subject
- Resulted in permanent impairment of a body structure or body function. Required in subject hospitalization or prolongation of existing hospitalization
- Resulted in medical or surgical intervention to prevent life threatening illness or permanent impairment to body structure or body function
- Led to fetal distress, fetal death, or congenital anomaly/birth defect

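### The primary SAE rate has only a per-protocol analysis set, and device failures and noncompliance are discarded with no exemption for safety, so a related SAE can drop out of it

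*Combined protocol and SAP*

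**What the plan says.** Section 10.3 sets one primary outcome, the "incidence of device or procedure related Serious Adverse Events (SAE), as adjudicated by the Independent Physician Adjudicator".

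Section 14.1.2 names one analysis set for it, which "will include all subjects who underwent C-Scan procedure per protocol". *Per protocol* is not defined there or elsewhere.

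Section 14.1.3, headed as the operational analysis set, says that the failures to be "discarded from the trial statistical analysis will include all cases where the system did not function as expected". It lists capsule operational failure, Track operational failure and "Subject's noncompliance with procedure requirements". It does not say that safety outcomes are exempt.

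Section 14.1.4 plans descriptive statistics and names no population. No all-treated, all-ingested or all-enrolled set is defined anywhere in the document.

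**The concern.** Membership of the primary safety set depends on what happens after the capsule is swallowed: whether the device worked and whether the subject complied. Device failure is one route by which a device can cause harm, so a rule that discards failures can discard the events the primary outcome is meant to count.

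The events themselves are not lost. Section 16.3 has all adverse events collected and reported, and section 16.4.2 requires prompt written SAE reports. What is at risk is the primary percentage. Because the plan does not say which reading of 14.1.2 and 14.1.3 applies, the choice could be made after the SAEs are known.

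**Working it through.** The plan gives no SAE rate, margin or interval to reproduce, and section 14.1.1 says the sample size (up to 45) does not come from a power analysis. The check is therefore a reading of the text followed by an illustration.

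**Can one subject be both a primary event and a discarded case?**

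1. *Safety malfunction.* Section 15.1.3.1 states: "In the case of Safety Malfunction, intervention is required to remove the capsule without delay". The intervention "may include: use of laxatives, fiber supplements, removal by colonoscopy, or by surgery". Under section 16.1.2 an SAE includes an event that "Resulted in medical or surgical intervention to prevent life threatening illness or permanent impairment to body structure or body function". Laxatives or fiber would not ordinarily qualify; some removals by colonoscopy or surgery could. Under section 16 the event would also have to start before bowel preparation for the colonoscopy. If all this held, the subject would have a related SAE and would also fall under the general clause of 14.1.3 about the system not functioning as expected.
2. *Retention.* Section 15.1.3 defines non-excretion beyond 300 hours as an SAE. Section 16.1.4 lists a stay of about 100 hours or more in the caecum as a device malfunction. A capsule held in the caecum past 300 hours meets both descriptions.
3. *Withdrawal.* Section 12.4 lets the investigator withdraw a subject for "Severe side effects clearly related to the study device or procedure" or for inadequate compliance. Section 14.1.2 does not say whether a withdrawn subject still counts. Severe is not the same as serious, so this matters only when the event is also an SAE.

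**Direction of the effect.** With S subjects having a related SAE among N, discarding d subjects of whom s have an SAE changes the rate from S/N to (S − s)/(N − d). The new rate is lower only if s/d > S/N, that is, if SAEs are more frequent among the discarded than among all subjects.

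**Illustration.** Assumptions: N = 45, all treated, and S = 1. Intervals are exact (Clopper-Pearson) two-sided 95%; with zero events the upper limit is 1 − 0.025^(1/n).

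| Case | Rate | 95% CI | Change |
|---|---|---|---|
| Nobody discarded | 1/45 = 2.2% | 0.06% to 11.8% | – |
| d = 1, s = 1 | 0/44 = 0% | 0% to 8.0% | −2.2 points |
| d = 5, s = 1 | 0/40 = 0% | 0% to 8.8% | −2.2 points |
| d = 5, s = 0 | 1/40 = 2.5% | 0.06% to 13.2% | +0.3 points |

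For the third row s/d = 1/5 = 20%, above S/N = 2.2%, so the rate falls. For the fourth row s/d = 0, so it rises.

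**How often would subjects be discarded?** This cannot be projected. Section 8.1 mentions two faulty capsules that were expedited and several technical malfunctions in the earlier study, but gives no total.

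**The case against.** The strongest reply is that the two sections describe different sets. Section 14.1.2 is expressly for safety and 14.1.3 is headed operational; *per protocol* may mean only that the subject had the procedure described in this document. Section 8.1 supplies a motive: earlier malfunctions harmed nobody but yielded no performance data, which is a reason to drop them from performance analyses. This reading is reasonable and may be what the sponsor intends. It is not written, however. The discard in 14.1.3 applies to the trial's statistical analysis without limit, and noncompliance is on the list although it is not a technical failure. Even if *per protocol* is read mildly, 14.1.3 still removes the cases.

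Second, the safety-malfunction example needs several conditions at once, and a Track that signals a fault is not plainly a Track failure. That is fair. The example works through the general clause or through capsule failure, and the retention overlap does not depend on it.

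Third, the earlier study reported no harm from malfunctions and no related SAE, so a downward bias is not demonstrated. That stands as a limit on certainty. With no related SAEs in any group, though, those data cannot show whether such events concentrate among failures. A downward bias remains the likelier direction, because a failure can itself lead to the intervention.

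Fourth, this is an unpowered, descriptive pilot with no threshold for the SAE outcome. It is true that no formal decision would flip. But the rate is the study's only primary result, and one case separates no related SAEs from one.

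**Conclusion.** The concern holds. As written, the only set for the only primary outcome can lose a subject with a related SAE because the device failed or the subject did not comply, and no text restores that subject to the rate. The size is unknown. In the illustration one lost event moves the result from 2.2% to 0%, while discarding five SAE-free subjects moves it up by 0.3 points. The numbers of SAEs and exclusions are assumptions. The conclusion about the text does not depend on them, but a fall in the rate requires SAEs to be more frequent among discarded subjects than overall. This should be corrected before any results are seen.

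**What to change.** Replace the second sentence of 14.1.2 with:

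> The primary safety set includes every subject in whom capsule ingestion was attempted, regardless of device malfunction, compliance, protocol deviation or withdrawal. Events with onset within the adverse event collection period of section 16 are counted. The incidence will also be shown among subjects who swallowed the capsule, with the number withdrawn before the end of that period.

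Add to 14.1.3:

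> These exclusions apply only to technical and performance outcomes and never to safety outcomes.

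The second denominator deals with dilution by failed ingestions. In the earlier study 3 of 66 subjects failed to ingest (section 8.1). If that carried over, an assumption, 3/66 × 45 = 2.0 subjects would fail here, and one SAE would read 1/45 = 2.2% or 1/43 = 2.3%. Subjects are connected to the Track before ingestion (section 13.5.1), so if the sponsor wants procedure-related events counted from connection, the set should start there instead. An exact 95% CI for the primary incidence would be useful but is optional (0/45 has an upper limit of 7.9%).

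The cost is wording only, using events already collected. Two limits remain: collection stops when bowel preparation starts, and section 12.4 states no follow-up after withdrawal, so for withdrawn subjects the count may cover only events up to that point. The reported SAE rate may be less favourable than under the present text.

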### 14.1.3 Operational Analysis Set

Technical or operational failures that will be discarded from the trial statistical analysis will include all cases where the system did not function as expected:

- Capsule operational failure.
- Track operational failure.
- Subject's noncompliance with procedure requirements

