and in another case it was initiated by the sponsor since the batteries in the capsule were already depleted and no additional benefit was expected from the procedure. In two other cases, drugs (*Picolax*) were used to expedite the expulsion of faulty capsules (that stopped working). In all four cases the total time was less than 200 hours. In one case the capsule was not retrieved by the patient at the end of the procedure and, probably lost in the sewage system. Abdominal X-ray on the following day confirmed that the capsule was expelled with no residual in the GI tract images. All cases were completed uneventfully.

Several adverse events were reported including one case of irritating sensation in the esophagus that lingered for hours after capsule ingestion, skin irritation (under the stickers), soft stool, abdominal pain, headache, radiation level (body dose) was significantly higher than the typical dose of 50 uSV and four cases in which the transit time was longer than 120 hours. Three SAE events occurred including one hemorrhage/hematoma seen on abdominal wall, one post-colonoscopy bleeding and one post-colonoscopy abdominal pain. All SAE were non-related to device or C-Scan procedure and resolved without medical intervention. Several technical malfunctions occurred during the study, none of which resulted in harm to the subject but did not provide any data regarding the performance of the C-Scan system. During the study, updates were made to the system software to continue to optimize the algorithm and the ability to collect additional physiological data.

This study demonstrated that the C-Scan procedure was safe as no device- related serious adverse event occurred in any C-Scan clinical trial and the procedure was well-tolerated by the participating volunteers. The primary end point of safety for the C-Scan system was demonstrated. The primary end point for performance in terms of Positive Percent Agreement resulted in 44% capsule vs 37% for FIT. The protocol target was set at 55%, hence superiority was demonstrated with a lower than expected result. The result of Negative Percent Agreement was 89% vs. a set target of 75%, hence target surpassed the expected result.

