### 10.4 Secondary Outcome Measures

- Subject compliance will be assessed by
  - Non-compliance rate throughout the study via diary completion by the subject Specific questionnaire completed by remote subject monitoring (via telephone)
- Subject satisfaction will be established by:
  - Designated questionnaire that focuses on patient's impressions regarding tolerance and potential safety concerns. Acceptance criteria was defined as average score >3.5 (1- low satisfaction to 5- high satisfaction), which represent high satisfaction with the safety and tolerance of the C-scan system.
  - Comparing patient's satisfaction with colonoscopy procedure.
- Collecting procedure related data:
  - Technical performance in normal daily routine.
  - Segmental transit time.
  - Procedure duration.
  - Bowel movements.
  - Agreement between C-Scan and colonoscopy with respect to the presence/absence of colonic polyp(s) [Note: C-scan data not to be used for clinical decision making in the care of patients, for this clinical study].
  - Inter-observer variability in the detection of significant clinical findings on a 'per patient' decision
- Battery life Assessment
  - Assessing adequate power supply for complete scan of the colon: length of capsule operation lifetime with respect to the lifetime specification of 100 +/- 10% hours.
- Device performance
  - Assessing colon model by the physician reviewers as presented on C-Scan View (e.g., normal, partial, right side missing, etc.).
  - Collecting data to improve the product's algorithm.

	Document Title	Clinical Investigational Plan For Study CL-SY-02-0096		
	Document No.	DOC001593	Revision	03

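### Section 14.1.3 discards capsule failures, Track failures and subject noncompliance without limiting the rule to any endpoint, although section 10.4 makes non-compliance rate and technical performance secondary outcomes

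*Combined protocol and SAP*

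**What the plan says.** Section 14.1.3 (Operational Analysis Set) contains only exclusions. It speaks of failures to be "discarded from the trial statistical analysis will include all cases where the system did not function as expected", followed by three bullets: capsule operational failure, Track operational failure, and "Subject's noncompliance with procedure requirements". It does not say which outcomes the exclusions apply to, and it sets no threshold for noncompliance.

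Section 10.4 lists the secondary outcomes. Compliance is to be assessed by "Non-compliance rate throughout the study via diary completion by the subject" and by a questionnaire administered by telephone. The procedure-related data include "Technical performance in normal daily routine". Device performance includes the reviewers' rating of the colon model, and the example ratings include a partial model and one lacking the right side.

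Two neighbouring sections might have limited the rule. Section 14.1.2 defines a set for the safety objective only. Section 14.1.4 promises descriptive statistics for every parameter but assigns no analysis set to any secondary outcome and asks for no table of exclusions. Separately, section 12.4 lets the investigator withdraw a subject for "Less than adequate compliance with the study routine", and the plan does not say whether such subjects remain in the compliance denominator.

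**The concern.** An exclusion rule should not be triggered by the event that an outcome counts. Here a capsule or Track failure is both a reason to drop the case and part of what a summary of technical performance should show. A lapse in compliance can likewise be both a reason to drop the subject and a unit in the numerator of the non-compliance rate. In each case the error makes the device or the procedure look better than it was.

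Compliance is a stated secondary objective of this pilot, and technical performance is a stated secondary outcome. If the rule is followed, the reported results depend on how many cases were discarded, and the report need not show that number. Section 14.1.4 gives counts with percentages, so an attentive reader might notice a shrunken denominator, but would not learn why it shrank.

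**Working it through.** The plan gives no expected failure or non-compliance rate, so it has no figure to reproduce. The check is a comparison of sections, followed by illustrative arithmetic.

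**Overlap for technical performance.** The first two bullets of 14.1.3 name capsule and Track failures outright. Any summary of technical performance made after the rule is applied contains none of them. Section 16.1.4 gives a wide definition of malfunction, including scanning that stops before the rectum and loss of tracking, but 14.1.3 does not refer to it. How far operational failure extends is therefore open.

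**Overlap for compliance.** Section 13.6.2 requires contrast and fibre three times a day. Section 13.6.3 has the diary record both. Section 10.4 measures non-compliance through that diary. A lapse that the outcome counts can thus also be a breach of procedure requirements under 14.1.3. How many lapses would meet both descriptions is not stated.

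**Size for compliance (counts assumed).** Let N be the subjects who ingested the capsule, m the noncompliant subjects, and d those of the m who are discarded.

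Reported rate = (m − d)/(N − d)

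| N | m | d | True rate | Reported rate |
|---|---|---|---|---|
| 45 | 9 | 1 | 9/45 = 20.0% | 8/44 = 18.2% |
| 45 | 9 | 3 | 9/45 = 20.0% | 6/42 = 14.3% |
| 45 | 9 | 9 | 9/45 = 20.0% | 0/36 = 0% |
| 45 | 5 | 3 | 5/45 = 11.1% | 2/42 = 4.8% |
| 45 | 14 | 3 | 14/45 = 31.1% | 11/42 = 26.2% |

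N = 45 is the maximum in section 14.1.1. In the earlier study (section 8.1), 63 of 66 subjects swallowed the capsule. At that rate 45 × 63/66 = 42.95, or about 43. With N = 43 and m = 9, the true 9/43 = 20.9% becomes 8/42 = 19.0%, 6/40 = 15.0% or 0/34 = 0% for d = 1, 3 or 9.

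**Is a capsule failure likely to occur?** Section 8.1 mentions two cases in which a drug was used to "expedite the expulsion of faulty capsules (that stopped working", among 63 completed cases: 2/63 = 3.2%. The exact (Clopper-Pearson) 95% interval is 0.4% to 11.0% (unrounded lower limit 0.387%). The chance of at least one failure in 45 capsules is 1 − (1 − p)^45:

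- lower limit: 1 − (1 − 0.00387)^45 = 16%
- upper limit: 1 − (1 − 0.110)^45 = 99%

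A failure is plausible, but its probability is close to unknown. The same section also reports several technical malfunctions without a number, so two is a minimum, not a systematic count.

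**If one or two capsules fail.** If technical performance were summarised as a failure proportion, the true figure would be 1/45 = 2.2% or 2/45 = 4.4%. After the rule is applied, no failure remains to report.

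**The case against.** The best defence is a narrow reading of 14.1.3. Its heading concerns an operational set, and its opening words concern cases in which the system did not work. The noncompliance bullet sits under those words and may mean only noncompliance that made the procedure fail. A missed diary entry is not a system failure. This reading is reasonable and shrinks the compliance effect: if one lapse in nine stopped the system, 20.0% becomes 18.2%. It does not remove the effect, and it does nothing for technical performance, where capsule and Track failures are excluded by name. The heading does not rescue the rule either, because the operative words refer to the analysis of the trial as a whole.

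A second defence is that section 10.4 lists technical performance as data to be collected and does not define it as a failure rate. That is correct, so the 2.2% and 4.4% above are only one way to express the loss. Any summary of technical performance is still incomplete without the failures.

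A third defence is that the trial is a descriptive, unpowered pilot with no acceptance threshold on compliance or technical performance. This limits the consequence: no test or error rate is affected. It does not make the estimates interpretable.

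Some stronger inferences are tempting, but the documents do not support them:

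- *Both rates must become zero.* For compliance this holds only if every counted lapse leads to discard, which 14.1.3 does not say.
- *Colon-model ratings are certainly biased.* They are affected only if partial or unreadable scans are classed as operational failures, and 14.1.3 is silent on that.
- *The earlier study gives a known failure rate of 3.2%.* Two cases picked out by the drug used to speed expulsion, in a study whose software was updated along the way, cannot support a precise forecast.
- *Battery-life or satisfaction results are biased in a known direction.* Nothing in the plan fixes a direction or size for either.

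**Conclusion.** The point holds for two secondary outcomes. As written, 14.1.3 removes capsule and Track failures from the summary of technical performance. It also lowers the reported non-compliance rate by an amount that depends on how many counted lapses lead to discard. For an assumed 20.0% among 45 subjects, the reported figure is 18.2% with one discarded and 14.3% with three. These counts are illustrative, because the plan gives neither an expected rate nor a threshold. An effect on the colon model is possible but conditional. No effect on the primary safety outcome is claimed under this point, since 14.1.2 defines a separate set for it.

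The conclusion rests on reading 14.1.3 as applying to every analysis for which no other set is defined. Nothing in 14.1.2 or 14.1.4 says otherwise for the secondary outcomes. The weakness is in the analysis rule and not in data collection, so it can be corrected before analysis.

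**What to change.** Amend section 14 as follows:

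- Limit the 14.1.3 exclusions to the image-reading outcomes: agreement of C-Scan with colonoscopy and FIT, and inter-observer variability. State what counts as an operational failure and as noncompliance for this purpose.
- Report technical failures by type over all subjects in whom ingestion was attempted.
- Compute the non-compliance rate over all subjects who ingested the capsule, including any withdrawn under 12.4 for poor compliance.
- In the colon-model summary, count partial or unreadable models as such.
- Tabulate the number of exclusions and the reason for each, by analysis.

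The cost is a few sentences of analysis text, one extra table and a little more analysis work, with no new data. The drawback for the sponsor is that reported compliance and device performance may look less favourable.
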